Participant Inclusion and Exclusion Criteria. Participant inclusion criteria are: (1) self-reporting moderate or higher pain on average during the last week (> 3 on a 0-10 pain intensity numeric scale), (2) self-reporting chronic pain related to cancer or its treatment, (3) completed active cancer treatment other than maintenance therapy, (4) being \geq 18 years of age, (5) functional fluency in English, and (6) mentally and physically able to participate and complete surveys. Participant exclusion criteria are: (1) a history of seizure disorder and (2) a significant brain injury or skull defect. Both exclusion criterion may impact qEEG measurement. We will not exclude potential participants based on use of pain medication, rather we will collect this information (drug, dose) and control for it in the data analysis.

Participant Recruitment. Staff at the SCCA Survivorship Clinic will screen Survivor Surveys completed by patients prior to their initial clinic visit from the past 2 years and during the study to identify patients who meet the pain intensity inclusion criteria. Names and contact information for patients will be given to the research team who will mail an information letter describing the study. The letter will include an opt-out postcard to be returned if the patient is not interested in being contacted by telephone about the study. Two weeks after the letters are mailed, patients will be contacted by telephone to further screen for eligibility and describe the study. If the patient is eligible and interested in participating, verbal and written consent to participate will be obtained. A study visit will be scheduled at the UW Health Sciences Center (HSC) for completion of the Stanford Hypnotic Clinical Scale and assignment of the intervention. The consent form and baseline questionnaires will be mailed to the participant to sign and complete respectively and return at the Week 0 (baseline) study visit.

Group Assignment. A SPSS randomization program will yield group assignments which will be placed in opaque, sequentially numbered sealed envelopes. Once the participant returns the completed baseline questionnaires and completes the in-person hypnotic clinical measure at the Week 0 study visit, the appropriate envelope will be opened and the participant will be notified of his/her group assignment. Based on their high or low hypnotic suggestibility score, eligible participants will be invited to participate in the qEEG study arm.

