2	Credibility/Expectancy Questionnaire 4-item questionnaire, test-retest 0.62-0.78, Cronbach's α 0.84-0.85. ⁶	Treatment outcome expectancy	X			
1	Demographic Questionnaire 15-item questionnaire.	Socio-demographics; cancer & treatment, and pain history; comorbidities; pain interventions	X			
3	Structured Interviews Each interview is anticipated to last 20 minutes and will be audio-recorded.	Barriers and facilitators associated with undergoing qEEG measurement; how intervention works				X

Data Collection Schedule and Procedures. Study Enrollment. The research assistant (RA) will contact potential study participants by telephone to screen, obtain verbal consent, and schedule the Week 0 study visit at the UW HSC. Baseline questionnaires and consent form will be mailed to the participant with instructions to complete 1-2 days before the Week 0 study visit.

Week 0 Study Visit. The RA will meet with the participant to (1) collect completed questionnaires and signed consent form; (2) administer the Stanford Hypnotic Clinical Scale; (3) share group assignment; (4) provide teaching about the RHI or relaxation recording, and participant study responsibilities; (5) administer the Credibility/Expectancy Questionnaire; and (6) inform participant if they are eligible for the qEEG measurement. Participants who are ineligible for the qEEG measurement (or eligible but not interested in participating) will begin using the assigned intervention at home on the same day as the Week 0 visit. The RA will schedule telephone calls with ALL participants to complete study measures at Week 2 (within 5 days of using the assigned intervention for 14 days), and Week 4 (within 5 days of using the assigned intervention for 28 days). Structured interviews with the RA also will be conducted by telephone. Participants will be reminded to return the Daily Diary in the provided pre-posted return envelope. Participants in the qEEG study arm will undergo the first qEEG at the Week 0 visit and begin using the assigned intervention at this time. All qEEG measurements

will take place at the UW Integrative Brain Imaging Center (IBIC). Week 2 and Week 4 qEEGs will be scheduled at the Week 0 visit and will take place within one day of completing study measures.

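### Follow-up pain scores appear to be collected by telephone by arm-aware staff, although self-completion, as at baseline, would be cheap

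*Combined protocol and SAP*

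**What the plan says.** All of this is in the combined protocol and SAP.

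- **Baseline.** Under Data Collection Schedule and Procedures (Study Enrollment): "Baseline questionnaires and consent form will be mailed to the participant with instructions to complete 1-2 days before the Week 0 study visit". Participant Recruitment agrees that the forms come by mail and are handed in at the Week 0 visit. Under Group Assignment, only after the forms are returned and the hypnotic measure is done does this follow: "the appropriate envelope will be opened and the participant will be notified of his/her group assignment".
- **Week 0 visit.** One role does every step: "The RA will meet with the participant to (1) collect completed questionnaires and signed consent form". The list goes on to "3) share group assignment; (4) provide teaching about the RHI or relaxation recording, and participant study responsibilities", and the same role administers the Credibility/Expectancy Questionnaire after assignment.
- **Follow-up.** "The RA will schedule telephone calls with ALL participants to complete study measures at Week 2" "and Week 4 (within 5 days of using the assigned intervention for 28 days"). The next sentence reads: "Structured interviews with the RA also will be conducted by telephone".
- **What is collected then.** Table 2a places PROMIS Pain Intensity 3a (the primary outcome) and PROMIS 29 (the secondary outcomes) at Weeks 0, 2 and 4. Under Data Analysis, Aim 1, the primary test is an ANCOVA of Week 4 pain intensity.
- **Diary.** Table 2b has a bedtime Daily Diary covering pain and anxiety, which participants return by post. Aim 1 plans only to graph it.

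**The concern.** Pain intensity is a subjective score, and participants are told their arm. Blinding cannot protect the score from the participant's own expectations, but the procedure can keep staff who know the arm out of the answer. Mailed baseline forms do that. At Weeks 2 and 4 the procedure becomes a telephone call, apparently with the role that disclosed the arm and gave the teaching.

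If that person prompts or clarifies differently by arm, or if participants answer that person differently by arm, the between-group contrast picks up a difference that is not a treatment effect. The Week 4 ANCOVA for pain and for all five secondary outcomes would be exposed. So would the Aim 2 moderator effect size, which rests on follow-up pain and is meant to size a larger study.

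**Working it through.** **1. Who elicits the follow-up scores?** The verb attached to the RA is schedule; the text never states who conducts the calls. Three features point to the RA:
- the calls are for the purpose of completing measures;
- the next sentence says interviews with the RA will also be by telephone;
- no other caller is named anywhere.

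The text also does not say whether the RA is one person. An RA who performed the Week 0 steps for a participant knows that participant's arm.

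**2. Is there a safeguard?** The documents mention no blinded assessor, no separation of teaching from assessment, no scripted reading of items and no self-completion at follow-up. The RA also enters the data, which the investigator verifies.

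**3. Baseline against follow-up.**

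| | Week 0 | Weeks 2 and 4 |
|---|---|---|
| Mode | mailed form | telephone call |
| Arm known to participant | no | yes |
| Arm known to staff involved | no | yes, if the RA calls |

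**4. The plan's own figure.** Table 1 inputs: 50 per group, 80% power, two-sided alpha 0.05, SD 1.0, 1.5 or 2.0. The two-sample t-test gives a detectable standardised difference of 0.566. Multiplied by the SDs, this is 0.566, 0.849 and 1.132, against the stated 0.57, 0.85 and 1.13. Table 1 reproduces, so its inputs can be used for illustration.

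**5. What a between-arm reporting shift would do.** The documents give no size for such a shift, so the values below are assumptions. With no true effect and an unadjusted t-test on 98 degrees of freedom:

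noncentrality = (shift / SD) / sqrt(2/50) = (shift / SD) / 0.2

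| Assumed shift (SD) | Points at SD 1.5 | Noncentrality | Chance of p < 0.05 | Share of 0.85 |
|---|---|---|---|---|
| 0 | 0 | 0 | 5% | 0% |
| 0.1 | 0.15 | 0.5 | 7.9% | 18% |
| 0.2 | 0.30 | 1.0 | 16.8% | 35% |
| 0.3 | 0.45 | 1.5 | 31.8% | 53% |

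The planned analysis is ANCOVA, not a t-test. If baseline and Week 4 scores correlate at 0.5 (also an assumption), the residual SD falls by the factor sqrt(1 - 0.25) = 0.866. The same shifts then give 8.8%, 20.8% and 40.3%. A more precise analysis detects a spurious shift more readily.

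This arithmetic applies to a reporting shift from any source. It does not show how much would come from the interviewer and how much from participant expectancy.

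**The case against.** The strongest counter-argument is the matched control. Both arms have the same RA role, the same teaching step, the same call schedule, and recordings of equal number, length and order. A wish to please the caller acts in both arms, and only a difference between arms biases the contrast. That stands. A reader might infer that the bias must favour hypnosis. The documents do not show this; nothing in them fixes a direction.

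A reader might also picture the caller as the participant's hypnotist. The investigator makes the hypnosis recordings; the RA gives teaching about the assigned recording in both arms. Nor do the documents state outright that the RA makes the calls or that the RA is a single individual.

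Nor does it follow that a positive result could never be told apart from an assessor effect. The Daily Diary, filled in at bedtime and posted back, is already a partial check on pain and anxiety, though a graphical one only. Treatment expectancy is measured too.

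Reference 3 might be offered in defence, since its title says that the method of administering PROMIS scales made no significant difference. On its title alone it concerns mode, not an interviewer who knows the arm.

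What remains is narrower: equal contact protects the comparison only if eliciting and answering do not differ by arm, and the plan contains no step to secure that.

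**Conclusion.** The point holds as a cheap improvement. On the natural reading, the self-reported primary outcome is elicited at Week 4 by telephone by staff who know the arm, after a baseline collected on mailed forms before allocation. That adds an avoidable possible source of bias to the participant expectancy that no change of mode can remove. Its size and direction are unknown. The rise from 5% to about 8%, 17% or 32% is conditional on assumed shifts of 0.1, 0.2 or 0.3 SD with 50 per group and an unadjusted test; it is not an estimate of what will happen. The conclusion rests on the RA, or other staff who know the arm, making the calls. If the sponsor intends a different caller, the plan should say so. The point does not show that the trial is invalid or that a positive result would be uninterpretable.

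**What to change.** 1. **Self-completion at follow-up.** Have the Week 2 and Week 4 PROMIS forms completed by the participant, through a REDCap survey (REDCap already manages the data) or on paper returned in a pre-posted envelope, as already supplied for the diary. Limit the RA call to a reminder. If items must be read by telephone, read them verbatim from a script, record the mode and the caller, and finish them before any structured interview.
2. **Diary sensitivity analysis.** Pre-specify a comparison of arms on mean Daily Diary pain over the last treatment week, for example days 22-28. Adjust for Week 0 PROMIS pain, because the diary has no Week 0 value. The baseline covariate then comes from a different instrument, so this supports the primary ANCOVA and does not replace it.

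**Cost.** Protocol and SAP wording, plus a REDCap survey or extra paper forms and postage. No extra staff are needed, and the diary data are already collected. The downside is somewhat more late or missing forms, which the reminder call and the recorded telephone fallback should limit. Forms collected by the fallback would still involve arm-aware staff, which is why mode and caller need recording. Participant expectancy remains and should be reported as a limitation.

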qEEG Protocol: The participant will complete a 0-10 pain intensity numeric scale pre- and post-qEEG. During the qEEG, the intervention group participant will listen to the RHI and the attention control group participant will listen to the relaxation recording via the MP3 player (Table 3). The EEG technologist will fit an electrode cap with premeasured sites using the international 10/20 system⁷ to the participant's head and the participant's scalp and will prep the earlobes with Nuprep (Weaver and Company, Aurora, CO, USA). The electrode sites will be filled with Electro-Gel (Electro-Cap International, Eaton, OH, USA) and prepped to ensure impedance values between 3 and 5 Kohms between each electrode site and each ear individually. The signals will be amplified using a bandpass of 0.53-70 Hz and sampled at the rate of 250 Hz. for 10 minutes (eyes closed) with an EGI Geodesic EEG System 300 using 128-channel HydroCel Nets. Participants will be monitored throughout the recording to ensure that they remain awake.

Per the UW IBC, raw recordings will be band-pass filtered between 0.5-100 Hz, and exported to Matlab (MathWorks, Natick, MA, USA) and then remontaged to the average reference montage. Plotted data will be inspected for potential artifacts (e.g., evidence of eye blinks, eye movements, body movements) and entire epochs will be removed if one or more channels exhibit presence of artifact. qEEG spectrum will be calculated from the first 2 minutes of artifact-free data with fast Fourier transform using 4-second epochs with 1/32 seconds of overlapping window advancement factor. The relative EEG power will be computed for each of five bandwidths (delta, 1.5-4 Hz; theta, 4-8 Hz; alpha, 8-13 Hz; beta, 13-30 Hz; gamma, 30-55 Hz), and the power estimates will be used for all subsequent analyses by our research team. Relative power measures show a closer correspondence to underlying cortical activity than does absolute power.⁸

All participants will receive \$50 for their participation, which will be distributed as follows: after return of the baseline

Table 3. qEEG Measurement Timeline

	Pre-Session	During Session	Post-Session
Week 0	10 minutes eyes closed	13 minutes RHI or relaxation	10 minutes eyes closed
Week 2	10 minutes eyes closed	13 minutes RHI or relaxation	10 minutes eyes closed
Week 4	10 minutes eyes closed	13 minutes RHI or relaxation	10 minutes eyes closed

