Aim 3: How does the RHI work? Compare brain states as measured by qEEG in cancer survivors with chronic pain receiving the RHI relative to the attention control condition (relaxation recording) at weeks 0, 2, and 4. We will use multiple regression models controlling for baseline scores and co-variates (e.g., medication use) to compare the change in theta activity from *pre-session* to *during session* between RHI and relaxation groups. We will also compare the change in theta activity from *pre-session* to *post-session* between groups. This will be replicated for all 3 time points: Weeks 0, 2, and 4. Replication allows us to assess if theta activity

changes during the study period. We will also explore other bandwidths (e.g., alpha, beta, delta, gamma) in our analysis. Medium or larger effect sizes for changes in bandwidth activity will be used to indicate that more formal testing in future research is warranted. *Explore the mediation effects of brain states (theta activity) on pain intensity at weeks 0, 2, and 4.* Cross-sectional analyses will examine mediation at weeks 0, 2, and 4 for how RHI and theta activity jointly affect pain intensity. The mediating effects model implicit in **Figure 1** will be tested using multiple regression models. Effect sizes (Cohen's d) will be computed for looking at the biological mechanism in a larger, more definitive study. *Structured interviews.* Transcribed interview data will be organized in ATLAS.ti7 (Scientific Software Development, Berlin, Germany). Content analysis^{10,11} will be used to understand the barriers and facilitators associated with undergoing qEEG measurement and perceptions on how the intervention works to reduce pain.

In summary, this study is extremely important because it will provide scientific evidence on the efficacy of a symptom self-management intervention that cancer survivors can easily use to manage a distressing symptom. Furthermore, this study is innovative in that it will increase our understanding of how this intervention works and who will most likely experience pain reduction when using this low-cost, accessible, and convenient intervention.

References

1. Morgan AH & Hilgard JR. (1978). The Stanford Hypnotic Clinical Scale for adults. *The American Journal of Clinical Hypnosis*, 21, 134-47.
2. [name] M. (2011). *Hypnosis for chronic pain management: therapist guide*. Oxford University Press.

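### EEG epochs are rejected by eye and the plan specifies no masking of the person doing it, so knowledge of arm could influence the Aim 3 theta contrast

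*Combined protocol and SAP*

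**What the plan says.** The qEEG Protocol section describes the processing chain from filtering to spectrum. Artifact is found by eye: "Plotted data will be inspected for potential artifacts (e.g., evidence of eye blinks, eye movements, body movements) and entire epochs will be removed". The removal trigger is that "entire epochs will be removed if one or more channels exhibit presence of artifact", and the recording is made "with an EGI Geodesic EEG System 300 using 128-channel HydroCel Nets". The data kept are fixed by order: "qEEG spectrum will be calculated from the first 2 minutes of artifact-free data", "using 4-second epochs with 1/32 seconds of overlapping window advancement factor". The section gives no amplitude threshold, automated criterion, second inspection or agreement check. It attributes the processing to the imaging centre's procedure, does not identify who inspects the plots, and passes the resulting power estimates to the research team for every later analysis.

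On what is played at the session, the same section says: "During the qEEG, the intervention group participant will listen to the RHI and the attention control group participant will listen to the relaxation recording". Masking of outcome assessment to arm, week or phase is not mentioned anywhere. The sealed envelopes under Group Assignment conceal the allocation only until they are opened.

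Data Analysis, Aim 3, compares the change in theta (pre-session to during, and pre-session to post) between arms at Weeks 0, 2 and 4, and then uses theta as a mediator of pain. Its decision rule is: "Medium or larger effect sizes for changes in bandwidth activity will be used to indicate that more formal testing in future research is warranted".

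**The concern.** Once the epochs are chosen, the theta value is pure computation. Choosing them is the one subjective step. If the person inspecting the plots knows the arm, or guesses it, borderline epochs may be treated more strictly in one arm or one phase. Where that strictness is related to theta, the retained mean moves and the shift looks like an effect of the recording.

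Leniency can matter too, because the outcome is relative power: artifact left in another band enlarges the denominator.

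Aim 3 is sensitive to this because it compares 10 people with 10 and acts on the size of an effect. What is at stake is a false signal, or a missed one, about whether theta is worth formal testing, and effect sizes carried into the planning of a larger study.

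**Working it through.** The documents give no sample-size, power or effect figure for theta (Table 1 concerns pain only), so there is no stated figure to reproduce. The check asks how far the rejections determine the data, how large a bias could be, and what it does to the decision rule.

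**Inputs from the documents.** 20 qEEG participants, 10 per arm (Design; the payment paragraph); 3 weeks and 3 phases; pre and post phases of 10 minutes and a listening phase of 13 minutes (Table 3); 4-second epochs; 2 minutes retained.

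**1. Room for selection.**
- Segments inspected: 20 × 3 × 3 = 180.
- Non-overlapping 4-second epochs available: 600/4 = 150 in a 10-minute phase and 780/4 = 195 in the 13-minute phase.
- Epochs' worth of data retained: 120/4 = 30, which is 30/150 = 20% or 30/195 = 15%.

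A rejected epoch is replaced by the next accepted one, so the rejections decide which data enter the spectrum.

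**2. Possible size of a bias (all assumptions).** Suppose epoch-level theta is roughly normal within a segment and a fraction q of epochs is dropped selectively in one arm's listening segments.
- If the dropped epochs are exactly those with the lowest theta, the mean rises by φ(z_q)/(1 − q) within-segment SD:
  - q = 0.05: 0.1031/0.95 = 0.109
  - q = 0.10: 0.1755/0.90 = 0.195
  - q = 0.20: 0.2800/0.80 = 0.350
- If the tendency to reject has correlation r with theta, multiply by r. Range taken: 0.3 to 1.
- To express the shift as d on the change score, multiply by k, the ratio of within-segment SD to the SD of the change score. Range taken: 0.5 to 2.

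| q | lowest (r = 0.3, k = 0.5) | highest (r = 1, k = 2) |
|---|---|---|
| 5% | 0.109 × 0.15 = 0.02 | 0.109 × 2 = 0.22 |
| 10% | 0.195 × 0.15 = 0.03 | 0.195 × 2 = 0.39 |
| 20% | 0.350 × 0.15 = 0.05 | 0.350 × 2 = 0.70 |

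**3. Effect on the decision rule.** Take medium as d = 0.5 (assumption; the plan gives no number). With n = 10 per arm, t = d × √(n/2), so d = 0.5 corresponds to t = 0.5 × √5 = 1.118 on 18 degrees of freedom. With no true effect and a bias b in SD of the change score, the probability of an observed d of at least 0.5 favouring RHI comes from the noncentral t with noncentrality b × √5.

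| b | P(observed d ≥ 0.5) |
|---|---|
| 0 | 0.14 |
| 0.06 | 0.17 |
| 0.11 | 0.20 |
| 0.20 | 0.26 |
| 0.35 | 0.38 |

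**4. Leniency, as an illustration.** If artifact adds 10% to total power outside theta (assumption), relative theta falls to 1/1.10 = 0.91 of its value, a loss of about 9%.

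**The case against.** A reader might infer that the person inspecting the EEG is unmasked, or that the laboratory knows which recording is being played. The documents do not say so; they are silent. The recording is played from an MP3 player, it is the research assistant who shares the group assignment and teaches its use, and nothing says that whoever runs the session also inspects the plots. The wording about the imaging centre suggests, without proving it, that the inspection is separate from the team testing the hypothesis. The supportable statement is that no masking is specified and the person inspecting is not identified.

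The plan also limits discretion. The any-channel rule states when an epoch goes, and the first-2-minutes rule prevents a free choice of later stretches. Inspection precedes the spectrum, so the judgement is made on traces and not on a theta value. Extra strictness unrelated to theta shifts nothing on average. All of this stands. It narrows the discretion without removing it, because calling an artifact is still a judgement, and a rule triggered by any one of 128 channels gives many occasions for a borderline call.

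A second tempting reading is that a bias near d = 0.70 is likely. That figure needs 20% selective removal, perfect selection on theta and the largest SD ratio together, and the direction favouring RHI is itself assumed. At 10 per arm the standard error of d is about √(2/10) = 0.45, so sampling noise outweighs a modest bias.

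Finally, Aim 3 is exploratory and its effect sizes only point to further testing. That limits the severity. It does not make the step harmless, because those effect sizes are meant to inform a larger study.

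**Conclusion.** The concern holds in limited form: a visual judgement decides which data give the theta values, and the plan contains no step that would keep knowledge of arm, week or phase out of that judgement. Whether any bias would occur, and how large it would be, cannot be derived from the documents. The ranges above rest on the assumed removal fraction, correlation and SD ratio. Small biases matter somewhat under the plan's rule: one of 0.11 raises the chance of a false medium signal favouring RHI from 0.14 to 0.20, and one of 0.2 raises it to 0.26.

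The consequence is confined to the Aim 3 theta contrast, the mediation model and the signal for future work. The primary pain outcome is unaffected. Severity: CONSIDER.

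**What to change.** Add to the qEEG Protocol:

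*Before inspection, exported segments are cut to a common length (for example, the first 10 minutes), given a random code without arm, week or phase, and presented in random order. Artifact removal is completed for all segments and the clean-epoch list is locked before the code is linked to arm. The number of epochs removed is reported by arm, week and phase.*

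The common length is needed because Table 3 gives 13 minutes for listening and 10 for pre and post, so renaming files alone would leave the listening phase recognisable. The rejection counts let others check for unequal strictness, which the present plan does not provide for.

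The cost is a short script, with no extra inspection, visit or procedure. Results cannot be viewed until screening is finished. The last 13 − 10 = 3 minutes of a listening segment would be unavailable if fewer than 2 clean minutes occur in its first 10. If the centre already inspects coded files, masking needs only to be written down.

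### Aim 3 interprets theta from relative power alone, so a between-arm difference in another band can shift it; log absolute theta and alpha should be reported beside it

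*Combined protocol and SAP*

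**What the plan says.** The qEEG Protocol section of the combined protocol and SAP states "The relative EEG power will be computed for each of five bandwidths". These run from delta to gamma and together cover 1.5 to 55 Hz. On how the results are to be used, the section says that "the power estimates will be used for all subsequent analyses by our research team". The reason given, with a citation, is that "Relative power measures show a closer correspondence to underlying cortical activity than does absolute power". The section does not say what total the relative power is a share of. It gives a filter range ("raw recordings will be band-pass filtered between 0.5-100 Hz") that is wider than the five bands.

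Under Data Analysis, Aim 3, regressions compare theta change between the arms, from before the session to during it and from before to after, at weeks 0, 2 and 4. The other bands are to be explored. The rule for taking a finding forward is "Medium or larger effect sizes for changes in bandwidth activity", with no number for medium. A further objective is to "Explore the mediation effects of brain states (theta activity) on pain intensity". No absolute-power or band-ratio analysis is named. Ten participants per arm have qEEG (five low and five high in suggestibility from each group, under Design).

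**The concern.** A relative power is one band divided by a total that includes the others, so its value moves when any band moves. Aim 3 nevertheless reads it as the activity of one band. Suppose the hypnosis recording lowers alpha more than the relaxation recording does, or the reverse. Relative theta will then differ between arms with no difference in theta power. Conversely, if one arm raises power in all bands by the same proportion, relative theta does not move at all.

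At stake is the mechanism reading. A difference that began in another band could be described as a theta effect, enter the mediation model, and inform the design of the larger study that Aim 3 is meant to prepare.

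**Working it through.** The plan gives no figure for Aim 3 to reproduce (Table 1 concerns pain scores). The size of the problem is therefore an illustration.

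**Inputs from the document:** relative power in five bands; 10 per arm; a medium effect as the threshold.

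**Assumed inputs:** the band shares, the size of the alpha change, the variability of change, d ≥ 0.5 for medium, and the sum of the five bands as the denominator.

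**1. Theta constant, alpha falls.** With theta share T, alpha share A and a proportional alpha fall f, the new theta share is T / (100 − fA), written as a percentage.
- T = 20, A = 40, f = 0.25: 20/90 = 22.2%, a gain of 2.2 points.
- Smallest over T = 15-25 and A = 30-50: 15/92.5 = 16.2%, a gain of 1.2 points.
- Largest over the same grid: 25/87.5 = 28.6%, a gain of 3.6 points.

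**2. Wider denominator.** Take delta/theta/alpha/beta/gamma at 25/20/35/15/5 and a 30% alpha fall (10.5 units).
- Five bands only: 20/89.5 = 22.3% from 20%, a relative rise of 11.7%.
- With 10 extra units outside the bands: 20/110 = 18.2% becomes 20/99.5 = 20.1%, +10.6%.
- With 30 extra units: 20/130 = 15.4% becomes 20/119.5 = 16.7%, +8.8%.

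The coupling weakens but remains.

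**3. Theta rises, but the rise is masked.**
- All bands up 20%: 24/120 = 20%, no visible change.
- Theta and alpha both up 20% from 20/40/40 (theta/alpha/rest): 24/112 = 21.4%. The same theta rise alone gives 24/104 = 23.1%.

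**4. What the other shares reveal.** From theta/alpha/rest of 20/40/40, a 25% alpha fall gives 22.2/33.3/44.4. A theta-only rise to the same theta share gives 22.2/38.9/38.9. The rest rises in the first case and falls in the second, so five shares read together can separate these two patterns. They cannot detect scaling common to all bands.

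**5. Effect on the go-forward rule.** With 10 per arm, d = 0.5 corresponds to t = 0.5 × √(10/2) = 1.118 on 18 degrees of freedom. Its upper tail is about 14%, so noise alone gives d ≥ 0.5 in about 14% of trials.

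The simulation used the shares in step 2, a between-person log SD of 0.3 per band, independent within-person log changes with SD 0.15 to 0.35, no mean theta change in either arm, and alpha multiplied by 0.7 in the RHI arm only.

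| Measure | Chance of observed d ≥ 0.5 |
|---|---|
| Relative theta, alpha fall in one arm | 36% (SD 0.35) to 73% (SD 0.15) |
| Log absolute theta, same data | about 14% |
| Relative theta, equal alpha fall in both arms | about 14% |

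**The case against.** The strongest defence has four parts.

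**The choice is deliberate.** The plan cites a reason for preferring relative power. That stands, and it supports keeping relative power as the main measure. The stated reason does not address dependence between bands.

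**The data are not uninformative.** A reader might infer that relative power cannot show which band moved, or that any theta finding would be an artefact. The documents do not support this. Shares preserve every between-band ratio, the other bands are to be explored, and the go-forward rule covers all bands. In simulations of a 25-30% alpha fall in one arm, the alpha effect (mean d −0.75 to −2.2) was larger than the spurious theta effect (0.29 to 0.98), so alpha would usually be flagged too. What remains is that no ratio or absolute measure is planned, and the mediation model uses theta alone.

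**The contrast is between arms.** An alpha fall common to hypnosis and relaxation largely cancels, so the distortion needs a differential change. The arms hear different recordings, so equality cannot be assumed, but a difference cannot be assumed either.

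**A weak check would not help.** Requiring only that relative and absolute theta move in the same direction would pass 58-89% of the false theta results in simulation, because the two measures share noise. The criterion has to be an effect size.

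Finally, Aim 3 is exploratory with about 20 people. That limits the consequence to the mechanism and mediation reading.

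**Conclusion.** The point holds as a cheap improvement to an exploratory aim. As planned, relative theta cannot by itself support a statement about theta power when another band changes differently between arms, and it cannot show a rise common to all bands. The planned exploration of the other bands is a partial safeguard.

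The sizes (1.2 to 3.6 points; 36-73% against about 14%) rest entirely on assumed shares, alpha changes, variability and a cut-off of d = 0.5. They show that the effect can reach the plan's own threshold, not that it will. It would also go too far to say that the shares sum to 100%: that is the natural reading, but the denominator is not stated. Nothing here touches the primary pain analysis.

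**What to change.** Keep relative power as the main measure and state its denominator. Then add to Aim 3, for example:

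*Log absolute theta power from the same artifact-free segments will be analysed with the same regressions and the same mediation model as relative theta. Effect sizes with confidence intervals for log absolute theta and log absolute alpha will be shown beside the relative ones. A result will be described as theta-specific only if log absolute theta also reaches the medium effect size. Otherwise it will be reported as a change in band distribution. A change in absolute theta without a change in relative theta will be reported as such.*

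The plan should also give the number that it means by medium.

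Requiring a medium effect on both measures cannot pass more false results than log absolute theta alone, about 14% in the illustration. That remaining rate reflects 10 per arm, and this change does not cure it.

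**Cost:** no new visits, participants or recordings. The absolute power from the Fourier step must be retained, since the plan names only relative power as what the team will use. There is one extra column of exploratory results and a stricter condition on wording.
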